Name of finished product: Areplivir, film-coated tablets	Volume: Pages:	
Active ingredient: Favipiravir		

The test drug is administered in hospital setting under supervision of a clinical investigator. The test drug is not handed over to the patient.
 
Arm 2 (n=100) patients receive standard therapy prescribed in accordance with the recommended treatment regimens included in the Interim Guidelines for the prevention, diagnosis and treatment of new coronavirus infection (COVID-19) approved by the Russian Ministry of Health (revision 6 dated 28.04.2020, or current revision at the time of patient enrollment) by decision of the investigator and taking into account the availability of drugs at the study site.
 
Standard therapy is administered in hospital setting.
 
Discharge of patients from a hospital is carried out in accordance with the local practice of the study site in compliance with the current sanitary and epidemiological regime.
		

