Sponsor: PROMOMED RUS LLC, Russia	Separate study table relating to part of the dossier	(For use by national authorized bodies only)
Name of finished product: Areplivir, film-coated tablets	Volume: Pages:	
Active ingredient: Favipiravir		
Investigational medicinal product, dose and mode of administration, batch number: Investigational medicinal product: Areplivir, film coated tablets (PROMOMED RUS LLC, Russia), batch 010520 (expiry date 06.2022). Patients in Arm 1 take the investigational product Areplivir, film coated tablets: on Day 1st of treatment - 1600 mg (8 tablets) 2 times a day; on days 2-14 of treatment - 600 mg (3 tablets) 2 times a day. The drug is taken orally every 12 hours, swallowing whole tablet without chewing and washing down with a glass of water. The course of treatment is 14 days. The test drug is administered in hospital setting under supervision of a clinical investigator. The test drug is not handed over to the patient.		
Duration of the study: The total duration of the study for the patient is not more than 31 days, of which the screening period is not more than 2 days. Visits: Visit 0 (screening, not more than 2 days); Visit 1 (randomization, day 1)*; Visit 2 (day 5); Visit 3 (day 10); Visit 4 (day 15)**; Visit 5 (day 21±1)***; Visit 6 (study completion, day 28±1)***. * Visit 1 may coincide with Visit 0. ** If a patient is discharged from hospital at an earlier date, the visit will be conducted at the time of discharge (for Arm 2 patients). *** If a patient is discharged from hospital at an earlier date, then this patient does not need to visit the study site. Fatalities and serious adverse events (SAE) will be followed-up through telephone contact with the patient. Discharge of patients from a hospital is carried out in accordance with the local practice of the study site in compliance with the current sanitary and epidemiological regime.		
Efficacy criteria: The efficacy of therapy is assessed using the following endpoints: Primary efficacy criterion: 
 • Time (in days) to improvement in clinical status by categorical ordinal scale of clinical status improvement. • Rate of clinical status improvement by categorical ordinal scale of clinical status improvement by 2 or more categories at Visit 3. Secondary efficacy criteria:		

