Sponsor: PROMOMED RUS LLC, Russia	Separate study table relating to part of the dossier Volume: Pages:	(For use by national authorized bodies only)																			
Name of finished product: Areplivir, film-coated tablets																					
Active ingredient: Favipiravir																					

 Percentage of patients with elimination* of COVID-19 according to PCR data at Visit 3. Time (in days) to end of fever (body temperature < 37.2 ° C for 3 consecutive days without antipyretic medication). Assessment of lung injury according to CT data at Visits 4, 5 and 6. Percentage of patients transferred to intensive care unit. Percentage of cases with non-invasive lung ventilation. Percentage of cases with mechanical lung ventilation. Incidence of fatal cases. 
* Elimination of the virus is defined as two negative laboratory results for the presence of SARS-CoV-2 RNA obtained at an interval of 24 hours.
 
Safety criteria:
 
 Total number of adverse events (AEs) stratified by severity and incidence; Incidence of adverse drug reactions; Incidence of serious adverse events (SAEs) associated with the use of the study drug/standard therapy; Percentage of patients with at least one AE; Percentage of patients who discontinuation treatment due to AE. 																					

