
Statistical methods:
 
Justification of sample size
 
The study will randomize 200 patients. Given the possible non-inclusion of patients at the screening stage, the maximum number of patients to sign the Informed Consent Form in the Patient Information Leaflet and to participate in screening will be no more than 210 people.
 
At the first stage, 40 patients are included in each study arm and the most sensitive efficacy criterion of the two selected is determined, or additional analysis is carried out to select the criterion from secondary ones. Given 40 patients in each of the study arms, the sensitivity of the study to confirm 15% superiority by incidence, supposing the expected response 80% in the test drug arm, will exceed 45%.
 
Two Independent Proportions (Null Case) Power
 
Analysis
 
Numeric Results of Tests Based on the Difference: P1 - P2 H0: P1 - P2 ≥ 0. H1: P1 - P2 = D1 < 0. Test Statistic: Z test with pooled variance
 
  
 	Sample Size Grp 1	Sample Size Grp 2	Prop H1 Grp 1 or Trtmnt P1	Prop Grp 2 or Control P2	Diff if H0 D0	Diff if H1 D1	Target Alpha	Actu Alpha	
   
 Power	0.4553	40	40	0.6500	0.8000	0.0000	-0.1500	0.0500	0.0500	
  
				Sample Size Grp 1	Sample Size Grp 2	Prop H1 Grp 1 or Trtmnt P1	Prop Grp 2 or Control P2	Diff if H0 D0	Diff if H1 D1	Target Alpha	Actu Alpha	Power	0.4553	40	40	0.6500	0.8000	0.0000	-0.1500	0.0500	0.0500
	Sample Size Grp 1	Sample Size Grp 2	Prop H1 Grp 1 or Trtmnt P1	Prop Grp 2 or Control P2	Diff if H0 D0	Diff if H1 D1	Target Alpha	Actu Alpha													
Power	0.4553	40	40	0.6500	0.8000	0.0000	-0.1500	0.0500	0.0500												

Sponsor: PROMOMED RUS LLC, Russia	Separate study table relating to part of the dossier	(For use by national authorized bodies only)
Name of finished product: Areplivir, film-coated tablets	Volume: Pages:	
Active ingredient: Favipiravir		

Said statistical power (45%) is acceptable for exploratory stages of the studies aimed to select the duration for endpoint monitoring and to select the endpoint at the second (confirming) stage.

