In case change of the planned endpoints, separate adjustment will be made for the multiplicity of comparisons and the required number will be recalculated at the second stage.

The total planned number of patients before the completion of the first stage will be 100 patients in each of the arms.

The estimated calculation until the data of the first stage are obtained is as follows. Given the available data from Chinese researchers, 15% superiority of favipiravir therapy over standard therapy without favipiravir is allowed in relation to the rate of improvement by 2 or more categories on categorical scale by day 10 of treatment. The adopted higher response to standard therapy of 70% is associated with a longer duration relative to the Chinese study (10 days instead of 7 days).

An RCT enrolling patients within 12 days of symptom onset found that favipiravir was superior to arbidol in terms of the clinical recovery rate at day 7 in patients with mild illness (62 [56%] of 111 with arbidol vs 70 [71%] of 98 with favipiravir), but not in those with critical illness (0 vs 1 [6%]). (Chen C. Huang J. Cheng Z. et al. Favipiravir versus arbidol for COVID-19: a randomized clinical trial. medRxiv. 2020; (published online April 15.) (preprint).

Tests for Two Proportions

Numeric Results for Testing Two Proportions using the Z-Test with Unpooled Variance

H0: $P_1 - P_2 \geq 0$ vs. H1: $P_1 - P_2 = D_1 < 0$.

Target	Actual	Diff						
Power	Power*	N1	N2	N	P1	P2	D1	Alpha
0.80170	107	107	214	0.6500	0.8000	-0.1500	0.0500	0.80

* Power was computed using the normal approximation method.

Thus, the minimum number of subjects required for a clinical study is 200 with 100 subjects randomized to each of the two groups.

Statistical analysis

The purpose of statistical analysis is to prove superiority of Areplivir, film-coated tablets (PROMOMED RUS LLC, Russia), over standard therapy in patients hospitalized with COVID-19.

The results of statistical analysis, descriptive statistics and illustrative tables, graphs, lists will be presented in interim and final clinical study reports.

General methods of analysis

Statistical analysis is carried out in accordance with the requirements of the Guideline for Good Clinical Practice (ICH 9) approved by the Eurasian Economic Commission, and other applicable requirements and laws.

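### Visit 4 moves to the discharge date for Arm 2 only, so the Visit 4 CT comparison can rest on different study days by arm; minor, direction and size unknown

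*Combined protocol and SAP*

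**What the plan says.** All references are to the Synopsis of the combined protocol and SAP.

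- **Duration of the study.** Visit 4 is day 15, Visit 5 day 21±1 and Visit 6 day 28±1. The Visit 4 footnote says that on earlier discharge "the visit will be conducted at the time of discharge (for Arm 2 patients"). The footnote to Visits 5 and 6 names no arm: on earlier discharge, "then this patient does not need to visit the study site". It adds: "Fatalities and serious adverse events (SAE) will be followed-up through telephone contact with the patient".
- **Discharge.** "Discharge of patients from a hospital is carried out in accordance with the local practice of the study site". No arm is named.
- **Arm 1 treatment.** The course lasts 14 days, and its setting is stated as follows: "The test drug is administered in hospital setting under supervision of a clinical investigator. The test drug is not handed over to the patient".
- **Secondary efficacy criteria.** "Assessment of lung injury according to CT data at Visits 4, 5 and 6". Analysis of secondary efficacy parameters compares the shares between arms by Fisher's exact or chi-square test. It names a visual scale for CT but gives no role to the day of the scan.
- **Safety Analysis.** Adverse-event (AE) frequencies are compared by the same kind of test. The Synopsis states no recording window.
- **Justification of sample size.** After stage 1 the more sensitive of the two primary criteria is chosen, or "additional analysis is carried out to select the criterion from secondary ones". If endpoints change, "separate adjustment will be made for the multiplicity of comparisons and the required number will be recalculated at the second stage".

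**The concern.** A comparison by visit label is fair only if the label means about the same study day in both arms. Here the plan itself makes it differ. An Arm 2 patient discharged on, say, day 10 has a Visit 4 scan on day 10, while an Arm 1 patient who completes the course in hospital is scanned near day 15. Lung injury on CT changes over time, so a difference in shares could come from timing rather than treatment.

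Two related gaps sit beside this. An Arm 1 patient who leaves before day 15 has no Visit 4 rule, and the 14-day course ends on day 14, so even a completer could fall into that gap. At Visits 5–6, discharged patients in both arms need not attend, so the scans come mainly from those still in hospital. That is a selection problem whatever the scan day.

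At stake are one secondary efficacy endpoint and, only if CT were promoted, the stage-2 criterion. A multiplicity adjustment or a recalculated sample size would not remove a timing or selection bias.

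**Working it through.** The documents give no figure on this point, so there is nothing to reproduce. Length of stay, CT course and a binary CT outcome are not stated. Every rate below is an assumption used for scale only.

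**1. Do the passages produce unequal scan days?** Supervised in-hospital dosing for 14 days explains why the footnote names only Arm 2. If Arm 1 stays, its Visit 4 is at day 15 and Arm 2's is earlier for every early discharge. If Arm 1 can leave early under local practice, its Visit 4 is undefined. Neither reading gives a common scan day.

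**2. Size of the gap in days.** With a share f of Arm 2 discharged on day d and Arm 1 scanned on day 15, the gap in mean Visit 4 day is f × (15 − d).
- f = 25%, d = 12: 0.25 × 3 = 0.75 days.
- f = 50%, d = 10: 0.50 × 5 = 2.5 days.
- f = 75%, d = 8: 0.75 × 7 = 5.25 days.

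**3. What a timing bias could do to the test.** Assume no true difference, 65% improved at day 15, and Arm 2 reduced by earlier scanning (two-sided 0.05, pooled Z, exact binomial).

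| Arm 1 vs Arm 2 | Significant, 100 per arm | Significant, 40 per arm |
|---|---|---|
| 65% vs 60% | 11% | 8% |
| 65% vs 55% | 31% | 15% |
| 65% vs 50% | 59% | 29% |

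**4. The opposite direction.** Suppose instead that 10% or 20% of Arm 1 leave unscanned and 90% of them would have improved. Scanned Arm 1 patients then show (0.65 − 0.09)/0.90 = 62.2% or (0.65 − 0.18)/0.80 = 58.75%, against 65% in Arm 2. The test is significant in 7% or 14% of trials (90 or 80 scanned against 100). Steps 3 and 4 assume different things about early leavers and should not be netted against each other. Together they show only that the sign is open.

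**5. How wide a two-arm sensitivity analysis can be.** Arm 2: half leave early with 45% improved at the scan and the rest show 65%, so 0.5 × 0.45 + 0.5 × 0.65 = 55% improved. The early and not improved are 0.5 × 0.55 = 27.5%, so day-15 status runs from 55% to 82.5%. Arm 1: 10% unscanned and 65% improved among the scanned gives 0.9 × 0.65 = 58.5%, up to 68.5%. The difference (Arm 1 minus Arm 2) runs from 58.5 − 82.5 = −24.0 to 68.5 − 55 = +13.5 points.

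**6. AEs, only if non-serious events are recorded no later than discharge.** At an assumed 3% per day in both arms, 1 − exp(−0.45) = 36.2% have an AE by day 15. If half of Arm 2 leave on day 10, Arm 2 records 0.5 × 36.2% + 0.5 × (1 − exp(−0.30)) = 31.1%. At 100 per arm the crude test is then significant in 12% of trials. With 70% leaving on day 9 the figures are 27.4% and 27%. If discharge is on day 14, rejection stays near 5%. These rates take discharge as unrelated to AE risk. If the lowest-risk patients leave first (simulated, gamma frailty with variance 1, 10,000 trials), the crude test rejects in about 5–6% and 11%.

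**7. Would time-to-event methods repair the AE comparison?** In the same risk-related setting the log-rank test rejects in about 9% and 12%, more than the crude test, and nearly always by making Arm 2 look worse. A day 1–5 window holds 5%. However, with a truly doubled AE hazard in Arm 1 (70% of Arm 2 leaving on day 9), power is about 58% in the window against 86–87% for log-rank. In about 30% of trials log-rank detects the harm and the window does not.

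**The case against.** The strongest reply is that the footnote follows from the dosing rules. Arm 1 is treated in hospital for 14 days, so an early-discharge rule is needed only for Arm 2, and an Arm 1 patient who leaves well before day 14 has stopped treatment. That stands as an explanation and narrows the Arm 1 gap to non-completers and those leaving just before day 15. The documents give no basis for putting 10–20% of Arm 1 there. It does not answer the CT point: the same dosing rules are what make scan day differ by arm.

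A second reply is that the endpoint is secondary and both primary criteria lie outside this footnote. That stands and sets the severity. Promoting CT at stage 2 is possible under the text but not likely.

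A third is that only a Synopsis is visible and it refers to a final SAP, so a common AE window may exist elsewhere. That also stands: the AE part is conditional, and deaths and SAEs are followed by telephone in any case.

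A reader might infer that earlier Arm 2 scans flatter Areplivir because they allow less time to resolve. The documents do not support that. Patients discharged early may be the better recovered, and Arm 1 patients who leave early may go unscanned.

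**Conclusion.** The point holds as a minor one. As written, the plan compares Visit 4 CT shares from different study days by arm whenever Arm 2 patients leave before day 15. It gives no Visit 4 rule for an Arm 1 patient who leaves before then, so the dosing-setting, discharge and footnote passages must be reconciled. CT at Visits 5–6 is selected in both arms.

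Neither direction nor size can be stated. The gap of 0.75 to 5.25 days and the rejection rates rest on assumed discharge patterns and an assumed binary CT outcome.

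It would go too far to conclude that the AE comparison is biased against Areplivir. That needs non-serious AE recording to stop at discharge, which the Synopsis does not say. Even then the effect is small if discharge is late or lower-risk patients leave first.

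**What to change.** Analysis and reporting only, with no change to discharge or dosing.

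1. Tabulate the actual Visit 4 scan day by arm, and the number and share scanned at Visits 4, 5 and 6 by arm. State how Visit 4 CT is handled for an Arm 1 patient discharged before day 15, once the passages are reconciled.
2. Treat the by-label CT comparisons at Visits 4–6 as descriptive. Add a Visit 4 sensitivity analysis that varies the day-15 status of two groups: Arm 2 patients scanned early and not improved, and unscanned Arm 1 patients. Report where the conclusion changes.
3. State that CT at Visits 4–6 will not be chosen as the stage-2 criterion on comparisons with unequal scan day or incomplete scanning.
4. AEs: state the recording window. If the full protocol records non-serious AEs to a common day, nothing more is needed. If not, report days of AE observation by arm beside the planned crude comparison and add, as a supplementary result only, the comparison over day 1 to Visit 2 (day 5). Do not substitute a log-rank test, and do not let the day-5 window override the full comparison: the first is biased when lower-risk patients leave first, and the second can discard a true late safety signal.

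The cost is a few sentences and tables, using scan dates and the last day of AE observation. The downside is that CT loses its confirmatory test and the sensitivity range may be wide, as in the worked example.

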- Percentage of cases with non-invasive lung ventilation.
- Percentage of cases with mechanical lung ventilation.
- Incidence of fatal cases.
- Assessment of lung injury according to CT data at Visits 4, 5 and 6.**

* Virus elimination is defined as two negative laboratory tests for SARS-CoV-2 RNA obtained at intervals of 24 hours.

**An "empirical" visual scale will be used to estimate changes in lung involvement from CT data.

For the analysis of these parameters, an intergroup comparison of shares is used using a two-sided version of the **Fischer's exact test** (or a two-sided version of the χ^2 (chi-square) test, if all the expected values in the cells of the contingency table for this analysis are 5 or more).

The protocol also includes the following endpoint:

- Time (in days) to fever disappearance (body temperature < 37.2 ° C for 3 consecutive days

Sponsor: PROMOMED RUS LLC, Russia	Separate study table relating to part of the dossier	(For use by national authorized bodies only)
Name of finished product: Areplivir, film-coated tablets	Volume: Pages:	
Active ingredient: Favipiravir		

without antipyretic medication).

For the secondary efficacy parameter "time (in days) to fever disappearance (body temperature < 37.2 °C for 3 consecutive days without antipyretic drugs), a comparison between arms is made using the *Student's t-test* or the *Mann-Whitney test* (depending on the nature of the distribution of quantitative indicators). Also, *Kaplan-Meier technique* and the construction of *survival tables* can be used as descriptive methods of study. The *Gehan-Wilcoxon test, the Cox-Mentel test or the Log-Rank test* can be used to compare the time (in days) to the disappearance of fever in the study arms.

Analysis of secondary efficacy parameters is performed in the ITT population (main analysis), and in the PP population (additional analysis).

In case of developing acute respiratory distress syndrome and the need to switch patient to mechanical ventilation, the investigational drug is canceled, but the patient is not withdrawn from the study. Patients are under follow-up until Visit 6, the data are taken into account to assess efficacy in the ITT population.

Safety Analysis

Safety criteria

Safety assessment includes the following parameters:

- Total number of adverse events (AEs) stratified by severity and incidence;
- Incidence of adverse drug reactions;

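### CT lung injury at Visits 5 and 6 is tested between arms in the ITT population, but discharged patients are not required to attend those visits, so the comparison is selected after randomisation

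*Combined protocol and SAP*

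**What the plan says.** All references are to the combined protocol and SAP, section 2, Overview (Synopsis).

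- **Endpoint.** Under Efficacy criteria, one secondary criterion is "Assessment of lung injury according to CT data at Visits 4, 5 and 6". Visits 5 and 6 fall on days 21±1 and 28±1.
- **Test.** Analysis of secondary efficacy parameters lists this CT item among the qualitative endpoints. It then says "For the analysis of these parameters, an intergroup comparison of shares is used using a two-sided version of the" Fisher exact test, or chi-square when expected counts allow. The main population is ITT, with PP as additional.
- **Attendance.** Under Duration of the study, the triple-asterisk footnote, attached to Visits 5 and 6 only, reads "If a patient is discharged from hospital at an earlier date, then this patient does not need to visit the study site". It continues: "Fatalities and serious adverse events (SAE) will be followed-up through telephone contact with the patient".
- **Discharge.** "Discharge of patients from a hospital is carried out in accordance with the local practice of the study site", subject to the sanitary and epidemiological rules in force. The trial is open.
- **Differences between arms.** For Visit 4 (day 15), the double-asterisk footnote says that after an earlier discharge "the visit will be conducted at the time of discharge (for Arm 2 patients"). Arm 1 receives a 14-day supervised course in hospital: "The test drug is not handed over to the patient".
- **Missing data.** LOCF is stated for the main endpoint, in patients who cannot complete the course of therapy. Otherwise the section promises only suitable methods and names none.

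**The concern.** The analysis section treats CT at days 21 and 28 as if it were available for the ITT population. The visit schedule does not require it from anyone who has gone home. Being in hospital on day 21 or 28 is a post-randomisation event, plausibly related to the state of the lungs and open to influence by treatment. Two groups formed by that event are no longer the groups that randomisation made comparable.

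Two of the three CT time points are therefore exposed to selection bias while carrying a p-value and an ITT label. The stake is larger than for an ordinary secondary endpoint. Under Justification of sample size, stage 1 may lead to a criterion being taken from the secondary ones, and stage 1 is also meant to settle the duration of endpoint monitoring. A distorted day 21 or 28 CT result could thus shape the confirmatory stage.

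**Working it through.** **1. The plan's own figures.** The synopsis gives no sample-size, power or discharge figure for CT. Its power figures concern responder proportions of 65% and 80%. The main one reproduces: with 107 per arm, SE = √[(0.65×0.35 + 0.80×0.20)/107] = 0.0602, and Φ(0.15/0.0602 − 1.645) = 0.802, against 0.80170 stated. It does not bear on this point.

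**2. Who has a CT at Visits 5 and 6.**

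| Patient's status at the visit | In the ITT set? | CT required? |
|---|---|---|
| In hospital | Yes | Yes |
| Discharged earlier | Yes, given one dose and data from one post-baseline visit | No; telephone follow-up of deaths and SAEs |
| Died earlier | Yes, on the same condition | Not possible |

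A telephone call cannot supply a scan. Patients who go on to mechanical ventilation are explicitly followed to Visit 6, so some of the sickest patients keep full follow-up while discharged patients do not.

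**3. Does a missing-data rule close the gap?** The LOCF rule names the main endpoint. Its next sentence speaks more broadly of efficacy measures, but only for the same patients, those who cannot complete therapy. A patient who finishes treatment and goes home does not trigger it. If it were stretched to CT, a Visit 4 scan would stand in for day 21 or 28, and in Arm 2 that scan may have been taken at an earlier discharge. The general sentence on missing data names no method.

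**4. Illustration only; every input here is assumed.** Let latent severity S be standard normal, with residual CT injury in the top 30% of S in both arms, so there is no treatment effect on CT. Let a patient remain in hospital when an index D = ρS + √(1−ρ²)·e lies in its top fraction r. The injury rate among those scanned is P(S high and D high)/r. Results from 2,000,000 simulated draws, which direct bivariate normal integration matches to about 0.2 points:

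| ρ | r = 10% | r = 20% | r = 30% | Difference, 10% vs 20% in hospital | Difference, 10% vs 30% in hospital |
|---|---|---|---|---|---|
| 0.3 | 50.2% | 45.7% | 42.7% | 4.5 points | 7.4 points |
| 0.5 | 65.3% | 57.5% | 52.2% | 7.8 points | 13.1 points |
| 0.7 | 81.8% | 71.5% | 63.4% | 10.3 points | 18.4 points |

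Differences are taken before rounding. The true difference is 0 throughout. In this model the arm with fewer patients left in hospital looks worse; swapping the arms reverses the sign. With 20% remaining in each arm and the same selection, the difference is 0, but the displayed rate is 46% to 72% against a true 30%.

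**5. Precision.** The approximate 95% half-width for a difference near 50% is 1.96·√(2×0.25/n): 14 points with n = 100 scanned per arm, 31 with n = 20 and 44 with n = 10. The smaller values of n are again assumptions.

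**The case against.** - **The footnote waives attendance; it does not forbid a scan.** This stands. A reader might infer that no discharged patient will have a CT at these visits. The text supports only that none is required. Voluntary returners would be a selected group too, so the comparison is not rescued.
- **Discharge is not a pure measure of recovery.** This stands. Local practice and sanitary rules may keep well patients in, so the scanned group is not simply the patients who failed to recover. The selection remains, but its strength is unknown.
- **The direction is unknown.** This stands. A reader might infer that the bias works against Areplivir, because faster recovery would leave only its worst cases. The documents do not support that. The in-hospital course in Arm 1 and the early-discharge provision for Arm 2 make equal discharge patterns unsafe to assume, but they concern discharge before day 15 and fix no direction at days 21 and 28.
- **A missing-data method might yet be applied, or set out elsewhere.** Possible: the synopsis refers to another section and to a final analysis plan. The text available names no method.
- **It is one of seven secondary criteria, and proof of superiority rests on the two primary endpoints.** This limits the consequence, and the Visit 3 responder analysis is not directly affected. The option to promote a secondary criterion after stage 1 is why the point still matters.

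**Conclusion.** The concern holds as an unreconciled conflict within the synopsis. CT at Visits 5 and 6 is assigned a between-arm ITT test, while the schedule guarantees the scan only for patients still in hospital. As written, that test does not compare randomised groups and can err in either direction.

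No size can be attached to the bias, because no discharge rates are given. The 4 to 18 points above show only that the mechanism can matter under the assumed shares in hospital, 30% injury rate and correlations; they do not estimate what will happen in this trial. The conclusion itself needs no numerical assumption, only that remaining in hospital occurs after randomisation and is related to lung status. It concerns Visits 5 and 6. Visit 4 has a different and lesser weakness, in timing. The change should be made, but the point does not undermine the primary analysis.

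**What to change.** Reconcile the visit footnote with the efficacy criteria and the secondary analysis section, as follows.

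1. Remove the between-arm test and any efficacy claim for CT at Visits 5 and 6.
2. Report those scans descriptively by arm, with the number scanned and the numbers discharged and dead by each visit.
3. State under Justification of sample size that CT at Visits 5 and 6 is not eligible for selection as the stage 2 criterion.
4. Keep the between-arm CT test at Visit 4, and report the actual day of that scan by arm, because the double-asterisk footnote lets it take place earlier, at discharge, in Arm 2 only.

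A ranked outcome covering all patients (death worst, then in hospital ordered by CT finding, then discharged alive) could be at most an optional sensitivity analysis. It makes open-label local discharge part of the endpoint, and it no longer measures lung injury alone.

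The cost is wording: no new scans, visits or patients. Two nominal secondary CT tests are lost, neither of which could be read as a randomised comparison.
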